The most frequent expected adverse effects with oral nitrite are dry mouth (infrequent), and nausea/abdominal pain/methemoglobinemia/flushing/headache/dizziness (rare).

Abuse Potential: No risk for abuse of AIR001 has been demonstrated.

Pregnancy Risk: Although nitrite exists widely in nature and human ingestion occurs daily in foodstuffs and through water sources, no human data exist on the safety of administration of nitrite during pregnancy or lactation. AIR001 and oral nitrite should not be administered to women who are pregnant or lactating. Effective contraceptive measures should be utilized by women of child-bearing potential who receive either form of nitrite. Given the ubiquitous nature

of nitrite in the environment and the short half-life of AIR001, prolonged contraceptive use after ceasing AIR001 inhalational use is unnecessary, and should be predicated on the clinical judgment of the subject's clinician.

2 Study Objectives

Aim 1: Determine whether treatment with NO₂⁻ in addition to ET for 12 weeks improves exercise capacity and hemodynamic reserve in HFpEF. Expired gas analysis, inert gas (C₂H₂) rebreathe, and echocardiography will be performed during rest and exercise to measure oxygen consumption (VO₂), CO, and hemodynamics before and after completion of 12 weeks of ET with NO₂⁻ vs ET with inhaled placebo.

- Our **primary hypothesis** is that combination therapy with ET and NO₂⁻ will be associated with greater improvement in peak VO₂ compared to ET plus placebo. Our **secondary hypotheses** are that ET and NO₂⁻ will lead to greater improvement in CO reserve (CO/VO₂ slope), peak workload, and exercise hemodynamics (lower echocardiography estimated pulmonary artery pressure and E/e' ratio).

[figure not shown]
Aim 2: Determine whether treatment with NO₂⁻ in addition to ET for 12 weeks increases daily activity levels and QOL, and reduces symptoms of effort intolerance during ET. Subjects will use externally worn accelerometer devices to track daily physical activity. Tolerability of ET will be assessed by Borg perceived effort and dyspnea scores. Large and small vessel endothelial function (brachial and digital arteries) and quality of life (QOL) will be assessed.

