3.1 General Design

This is a Phase 2 randomized, double-blind, parallel group placebo-controlled trial testing whether inorganic sodium nitrite, as compared to placebo, can enhance the benefits from chronic exercise training (ET) in subjects with HFpEF (see flow diagram below).

Inorganic Nitrite To Amplify the Benefits and Tolerability of Exercise Training In Heart Failure With Preserved Ejection Fraction

Revised 16 Jan 2019

The total duration of the trial is 14 weeks.

Subjects will be screened from the inpatient and outpatient heart failure services and interested qualified subjects will be offered participation. Once consent has been obtained baseline assessment of cardiovascular function and exercise capacity will be performed. All subjects will undergo 12 weeks of ET. Participants will be randomized to receive sodium nitrite 3 times daily or matching placebo 3 times daily during the study period.

In Stage I this was with inhaled medicine for the full 12 weeks of ET. In Stage II, study drug will be administered using an oral preparation for the full 12 weeks. Study subjects will wear accelerometry devices to track daily activity levels at home.

At the Screening visit, during consent, subjects will be given the option to participate in an optional MRI sub-study where they will be asked to complete 2 Magnetic Resonance Imaging (MRI) scans. One scan will be completed prior to or as close as possible to the beginning of cardiac rehabilitation, the other within 2 weeks of completing week 12 of ET (for Stage II). A hematocrit will need to be obtained prior to the MRI if not already drawn within the past 30 days. We will evaluate adipose tissue content and cardiac structure and function. We will determine whether these variables relate to exercise capacity/intolerance in participants, and evaluate how they change with ET with or without nitrite. Subjects will be excluded from this optional substudy if they have contraindications to MRI including aneurysm clips, cardiac pacemakers, internal defibrillators, severe claustrophobia and pregnancy. Women of childbearing potential will undergo a urine pregnancy test; positive test results will yield exclusion from study participation. Patients will be excluded for contraindications to gadolinium-based MRI contrast material, namely glomerular filtration rate less than or equal to 30ml/min.

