3.2 Primary Study Endpoints

Exercise capacity assessed by peak oxygen consumption (VO₂) achieved during exercise testing will be the primary endpoint for Aim 1. Chronic activity levels assessed by accelerometry will be the primary endpoint for Aim 2. Assessments were performed after 12 weeks of intervention.

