Medidata, Rave, and Balance will be used for clinical data management and randomization. These tools are institutionally supported and allow for rapid database development. The implementation of the software within a project includes training on the system's use, robust error checking, security considerations, and full audit trail. Balance, which is integrated into *Rave*, allows for a variety of randomization and minimization algorithms.

54 Preparation and Administration of Study Drug

Drug dispensing will be managed by the research pharmacy who will obtain and store supplies from the contracted drug supply vendors for both the inhaled and oral nitrite/placebo formulations. At baseline, week 4, and week 8 study visits, participants will receive a sufficient supply of inorganic nitrite or placebo to permit three doses a day for 4 weeks (Stage I). At baseline, and week 4 participants will receive a sufficient supply of inorganic nitrite or placebo to permit three doses a day until final visit (Stage II). To account for potential damage or loss of drug, additional study drug doses will be supplied.

Participants will be instructed to take the medication as required by the protocol, and compliance will be discussed weekly with the participants and assessed every other week (at the time of QOL assessment). Adherence with the inhaled nitrite formulation will also be assessed by download of the compliance data from the nebulizer device, with oral nitrite adherence will be assessed by pill

Inorganic Nitrite To Amplify the Benefits and Tolerability of Exercise Training In Heart Failure With Preserved Ejection Fraction

Revised 16 Jan 2019

counts. Participants will be instructed to bring the nebulizer (Stage I only) and unused drug supplies (inhaled or pills) to study visits where drug is dispensed.

55 Subject Compliance Monitoring

Inhaled nitrite (Stage I): The I-neb device has a Participant logging system that automatically records adherence and compliance with protocol-specified treatments. The device log was reviewed every other week by the research coordinator with study participants to optimize adherence in Stage I.

Oral nitrite (Stage II): Administration of the oral capsule form of nitrite is expected to be much easier for participants compared with the inhaled delivery system in Stage I. Adherence will be encouraged through phone calls with participants and monitored by pill counts at weeks 4, 8, and 12.

56 Prior and Concomitant Therapy

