5.9.4 Return or Destruction of Study Drug

Participants are instructed to return all used, partly used and unused trial product at the 12 week visit (4, 8 and 12 week visit for Stage I, which has been completed). Returned trial product(s) (used, partly used or unused including empty packaging material) must be stored separately from the non-allocated trial product(s) until drug accountability has been reconciled. The investigators will keep track of all received, used, partly used and unused trial products.

6 Study Procedures

6.1 Screening Visit 1

At Visit 1, patients will provide written informed consent followed by history and physical examination performed by a cardiologist. Medications will be documented. Participants will complete a blood draw in the CRTU where (NT-proBNP levels, blood methemoglobin, blood sulfhemoglobin, fasting blood glucose and insulin levels will be tested. An optional blood collection drawing an additional 20mL's of whole blood will be collected, separated into serum and plasma by the CRTU and stored by BAP. This will be done at both the screening and final visits and stored for additional testing. We are storing the blood for future analysis and will be examining circulating inflammatory biomarkers, adipokines and how they relate to adipose tissue and HFpEF symptom severity. Assays to be run at a later date will include (subject to change): C-reactive protein (C-RP), Interleukin-3 (IL-1 β), Interleukin 6 (IL-6), Leptin, and Adiponectin. Assessment of endothelial function, baseline echocardiography, dual energy X-ray absorptiometry (DEXA) and a QOL assessment consisting of the KCCQ and SF 36 will be performed. Maximal effort cardiopulmonary exercise testing with expired gas analysis will then be performed with simultaneous echocardiography. Borg symptom severity (effort and dyspnea scores) will be recorded during standardized exercise training at a common objective workload, 2 mph on treadmill at 2° grade for 5 minutes.

Following visit 1 assessments, subjects will be instructed on the use of accelerometer (AXM) devices and devices will be dispensed. Participants are to wear AXM at all times starting at Visit 1. Participants will be randomized in a double-blind fashion at the time but will not start active treatment, and study drug will not be dispensed until the first ET visit (below).

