Measurement of QOL will be performed every other week at ET sessions using the Kansas City Cardiomyopathy Questionnaire (KCCQ).^{56, 57} The KCCQ score reflects clinical status in HF with high fidelity;^{56, 57} the score changes rapidly with clinical improvement or deterioration,^{58, 59} is strongly associated with outcome,⁶⁰ and performs equally well in HFpEF and HFrEF.⁶¹ The SF36 will be completed at the screening visit and final endpoint visit (week 12).

Endothelial function will be assessed at Visit 1 and Visit 2 using digital arterial tonometry (reactive hyperemia peripheral arterial tonometry, RH-PAT, EndoPAT, Itamar Medical).⁹ These noninvasive assessments are routinely performed for both research and clinical care purposes. Changes in activity level, QOL and symptoms will then be correlated with changes in microvascular endothelial function (RH-PAT).

Assessment of Exercise capacity will be performed at Visit 1 (pre drug) and Visit 2 (week 10 for Stage II of study) using expired gas analysis in the laboratory of [name] (Joseph 4).

Subjects participating in the additional ancillary study will also undergo an additional cardiopulmonary exercise test at the final ancillary study visit. Participants will undergo standard, maximal effort cardiopulmonary testing on a semi-recumbent cycle ergometer to maximal subjective effort level with assessments of gas exchange as described below:

- Measurement of Gas Exchange and Ventilation will be performed during exercise testing to measure the volumes of VO₂, carbon dioxide produced (VCO₂), breathing frequency (fb), tidal volume (VT), minute ventilation (VE), partial pressure of end-tidal oxygen and carbon dioxide (PETO₂ and PETCO₂), and derived variables (e.g., respiratory exchange ratio, VE/VCO₂, etc.) using a low resistance, open circuit, automated metabolic system (Medical Graphics Co., St. Paul, MN) integrated to a mass spectrometer (Perkin Elmer, model 1100) as we have previously described.^{4,9,13,35,36}
- Cardiac Output (CO) will be measured at rest and during exercise by the acetylene (C₂H₂) wash-in technique first described by Stout et al., refined by Gan et al. and Nielson et al. and validated against direct Fick in our laboratory.⁴⁵⁻⁴⁸

Echocardiography will be performed at rest and during exercise at Visit 1 and Final Visit to estimate central cardiac hemodynamics and ventricular function, including EF, Doppler-estimated pulmonary artery systolic pressure, and LV filling pressures (E/e' ratio).

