7.3 Primary Outcome Analysis

Primary Statistical Hypotheses:

H0: Change from baseline to 12 weeks in Peak VO₂ in participants randomized to NO₂⁻ will be equal to the change in Peak VO₂ in participants randomized to placebo.

Ha: The change from baseline to 12 weeks in Peak VO₂ will be different between the two randomized groups

Analysis Summary:

The primary statistical hypothesis will be tested using a regression framework. The dependent variable will be the change (baseline to 12 week) in Peak VO₂. An indicator variable will be used to indicate the randomized treatment assignment (NO₂⁻ vs. placebo as the referent). This analysis is equivalent to a two-sample t-test. While the study design is randomized, the number of participants is relatively small, so imbalance between putative confounding variables may be observed. To address this, we will conduct an a priori sensitivity analysis that will adjust for baseline Peak VO₂, BMI, Sex, and Age group strata through an extension of the regression model used for the primary analysis. The type III estimate of the treatment effect will be compared to the unadjusted estimate to assess the robustness of the randomization process.

Statistical testing for the primary analysis will be two-sided at the alpha=0.05 level of significance.

8 Safety and Adverse Events

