15.1 Schedule of Assessments

	A	B	C	D	E	F	G	H	I	J	K	L	M	N
1							Primary Study:							
2	Visit windows	Screening Visit/ Day -7	Day -14	Baseline Visit/ ET 1/Day 0	Phone f/u Day 1 to 2	Weeks 1 - 3	Wk 4	Weeks 5 - 7	Wk 8	Week 9	Week 10	Final Visit/Week 12	2 Week f/u Visit	Wks 37 to 46 ^c
3	Informed Consent	X												
4	Medical Hx	X												
5	Medication Review	X					X		X			X		
6	Physical Exam	X										X		
7	NYHA class	X										X		
8	CPET	X										X		X
9	Hemodynamic Echo	X										X		
10	Lab evaluation ^a	X					X		X			X		
11	Pregnancy Test	X										X		
12	DEXA Scan	X										X		X
13	Endothelial Function (Endopat)		X									X		
14	QOL assessment (KCCQ)	X	X			Wk 2	X	Wk 6	X		X	X		X
15	IPAQ	X										X		
16	SF-36 Questionnaire	X										X		X
17	Randomization	X												
18	Study Drug Education	X	X											
19	Dispense Study Drug		X					Wk 5						
20	Collect un-used study drug						X		X			1x/wk		
21	Study drug compliance assessment and education			X	1x/wk	1x/wk	1x/wk	1x/wk	1x/wk	1x/wk				
22	Study drug accountability/ pill counts											X		
23	Accelerometer Education	X												
24	Dispense / Exchange / Return accelerometer	X					X		X			Wk 12		X ^b
25	Accelerometer Data download						X		X			Wk 12		X ^b
26	Exercise Training		X		3x/wk	3x/wk	3x/wk	3x/wk	3x/wk	3x/wk				
27	Borg Symptom Severity & Exercise Tolerance	X			1x/wk	1x/wk	1x/wk	1x/wk	1x/wk	1x/wk	X			X
28	AE assessment		X	X	1x/wk	X	1x/wk	X	1x/wk	1x/wk	X	X		X
29	Optional MRI Study	X (1)										X		X
30	Optional whole blood, lab draw study	X										X		X
31		ANT pro BNP, sulfhemoglobin, methemoglobin, fasting blood glucose and insulin levels. (1)Optional MRI will be performed prior to or as close to the start of exercise as scheduling allows.		^a Phone call to take place if not participating in the ancillary study	^b Participants randomized to behavioral/motivational intervention will have once weekly visits with investigator and 2 phone visits per week	^c Exchanged/Dispensed Pleium accelerometer and download data								IRB 16-001467 V11 Nov. 2019

15 Attachments

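### The assessment text still dates the Stage II peak VO₂ test at week 10, while the endpoint, hypothesis and schedule all use week 12

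*Combined protocol and SAP*

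**What the plan says.** The Study Assessments text that follows Section 6.5.3 sets the timing of the cardiopulmonary exercise test: "Assessment of Exercise capacity will be performed at Visit 1 (pre drug) and Visit 2 (week 10 for Stage II of study". This is current procedure text, and it names Stage II.

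The rest of the current protocol points to week 12:

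- Section 2, Aim 1, has the measurements taken at rest and during exercise, including oxygen consumption and "hemodynamics before and after completion of 12 weeks of ET".
- Section 3.1: "In Stage II, study drug will be administered using an oral preparation for the full 12 weeks".
- Section 3.2, on the primary endpoints: "Assessments were performed after 12 weeks of intervention".
- Section 5.5, on Stage II adherence: "monitored by pill counts at weeks 4, 8, and 12".
- Section 5.9.4: "Participants are instructed to return all used, partly used and unused trial product at the 12 week visit".
- Section 7.3: "The dependent variable will be the change (baseline to 12 week) in Peak" VO₂. The Study Summary uses the same interval.
- Section 15.1: the on-trial follow-up exercise test falls under "Final Visit/Week 12".

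Section 6.4 places the Stage II exercise test at the Final Visit. Its opening sentence gives a week for that visit (week 12) for Stage I only, although a later sentence refers to the final training visit as week 12 with no limit to one stage.

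Section 1.0 explains where week 10 came from. The previous modification shortened the period before endpoint assessment from 12 to 10 weeks, and the current one restores 12 weeks of treatment to match Stage I.

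**The concern.** The procedure text and the analysis text give different weeks for the same primary measurement. Staff who follow the assessment line would collect a 10-week change, while Section 7.3 tests a 12-week change.

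The mismatch matters more here than in a simple parallel design because the comparator is pooled. Section 7.2 combines 17 Stage I inhaled-placebo patients with 17 Stage II oral-placebo patients, against 34 Stage II nitrite patients. A Stage II test at week 10 would put all of the nitrite group, but only half of the placebo group, on the shorter training period.

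There is also a question of fact. Section 1.0 reports 14 patients enrolled under the earlier modification, the one that used 10 weeks. The text reviewed does not say at which week they had their endpoint test.

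**Working it through.** **1. Side-by-side check of the week.** Section 6.2 sets three training sessions a week. Week 10 ends at session 3 × 10 = 30 and week 12 at session 3 × 12 = 36. The exercise-tolerance paragraph of Study Assessments runs the weekly Borg tests up to session 36 and then lists Visit 2. On that reading Visit 2 follows week 12, so the exercise-capacity paragraph, which puts Visit 2 at week 10, conflicts with its own neighbour. The quality-of-life paragraph just above it also calls the final endpoint visit week 12. A week-10 test would miss 36 − 30 = 6 of 36 sessions.

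**2. Does the plan's own sample size depend on the week?** The inputs from Section 7.2 are difference 1.5, SD 2.2 (the exercise-training arm of the cited trial), two-sided alpha 0.05 and power 80%. By the normal approximation:

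n per group = 2 × (1.960 + 0.842)² × 2.2² / 1.5² = 33.8, rounded up to 34.

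The stated 34 is reproduced. No visit week enters the formula, so correcting the line changes no sample-size figure.

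**3. Scenario for the bias.** The documents give no curve of training gain over time, so the following are assumptions:

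- the 2.3 ml/kg/min training gain cited in Section 7.2 is the 12-week gain in both arms;
- a share f of it falls after week 10;
- the nitrite effect is complete by week 10;
- every Stage II patient is tested at week 10;
- the model has only a treatment indicator, as in Section 7.3.

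The nitrite group then loses 2.3 × f. The pooled placebo group loses 2.3 × f × 17/34, because only its Stage II half is tested early. The bias against nitrite is the difference:

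2.3 × f × (1 − 17/34) = 2.3 × f × 0.5

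| f | Bias against nitrite (ml/kg/min) |
|---|---|
| 0 (gain complete by week 10) | 0 |
| 1/12 | 0.10 |
| 1/6 (linear over 12 weeks) | 0.19 |

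The last row is 0.19/1.5, about 13% of the target difference. It is not an upper bound: f would exceed 1/6 if the gain came late.

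**4. Same scenario within route.** The Study Summary says that testing will be stratified by route. Both oral arms would then be tested at the same week, the training shortfall cancels, and the bias is close to 0. If the nitrite effect were still growing after week 10, the analysis would estimate a 10-week effect instead of a 12-week one.

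**The case against.** The strongest reply is that the document resolves the conflict itself. The endpoint, hypothesis, dependent variable, Stage II treatment duration, pill counts and schedule agree on week 12, and Section 1.0 states that the period was restored to 12 weeks. The assessment line is one of several that bear on the timing, and the schedule gives the week of the final visit directly. All of this stands. It shows that the intent is recoverable, but it does not remove an explicit contrary instruction for the primary measurement.

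Three stronger readings are tempting, and the documents do not support them:

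- A reader might infer that the Stage II endpoint time is undefined. It is not; one line is out of step with the rest.
- A reader might take 13% of the target effect, or a loss of power calculated from it, as the expected harm. It needs every assumption in step 3 of the working, including a model that ignores the stratification by route in the Study Summary.
- A reader might infer that the 14 earlier patients were tested at week 10, or use the counts in Section 1.0 to work out how many contribute complete data. The text reviewed gives no test week for them. The counts are not explained either: 51 required less 14 enrolled is 37, but the text asks for 47 more. Analysis sets and missing data are left to a supplementary SAP that is not part of the text reviewed and may deal with these patients.

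**Conclusion.** The contradiction is real and sits in current procedure text. As written, the line would have the Stage II primary endpoint measured at a different week from the one analysed, and two weeks earlier than in the pooled Stage I placebo patients. It should be corrected, but it does not undermine the design, since the intended week is clear and neither the sample size nor the hypothesis depends on the line.

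The size of any bias cannot be derived from the documents. About 0.19 ml/kg/min against nitrite applies only if all Stage II patients were tested at week 10, the analysis were unstratified, training gain accrued linearly and the nitrite effect were complete by then. Within route it would be close to 0. Whether any patient was in fact tested at week 10 is unknown from the text.

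**What to change.** - Reconcile the exercise-capacity paragraph of Study Assessments with Sections 3.2, 7.3 and 15.1, so that one time point governs the primary test in both stages. The stated hypothesis uses week 12.
- Extend the opening sentence of Section 6.4, which now dates the Final Visit for Stage I only, to cover Stage II.
- Record the actual week of the endpoint exercise test for every Stage II patient, including the 14 enrolled under the earlier modification. If any week-10 tests exist, report the primary result with and without them.

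The cost is two small text corrections, one data field and, only if needed, one sensitivity analysis. The sample size, hypothesis and analysis variable stay as they are.

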7.1 Statistical Overview

7.2 The full statistical details for this protocol are documented in the supplementary Statistical Analysis Plan (SAP). This protocol provides the key information, namely the justification for the sample size and the details on the primary analysis. The details regarding secondary endpoints, subgroup analyses, missing data and analysis sets are provided in the SAP. **Sample Size Determination**

In the RELAX trial, the mean \pm SD change in peak VO₂ with placebo in subjects with HFpEF treated for 6 months was 0 ± 2.0 ml/kg/min,³⁶ and in a previous trial of ET in HFpEF, the increase in peak VO in the ET arm was $+2.3\pm 2.2$ ml/kg/min.²² An increase of 75% (additional 1.5 ml/kg/min) in this change would be considered clinically relevant. Thus, we estimate that a sample size of N=34 participants per group will be required to provide 80% statistical power (two-tailed, alpha=0.05) to detect the difference of 1.5 ml/kg/min between subjects randomized to NO₂⁻ with ET versus placebo with ET. To account for attrition, we will increase our number of randomized subjects to 40/group (enroll 80 subjects total to accrue 68 total or 34 in each group).

Stage 1 was discontinued early because of loss of inhaled nitrite availability, therefore we will accrue a total of 68 patients with complete data combining the patients with complete data receiving inhaled placebo in Stage I (n=17) with another 51 patients in Stage II (17 receiving placebo and 34 receiving nitrite) to ensure that the study is adequately powered to test the study hypotheses.

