9.4	RECORDS RETENTION	41
10	STUDY MONITORING, AUDITING, AND INSPECTING	41
10.1	STUDY MONITORING PLAN	41
10.2	AUDITING AND INSPECTING	42
11	ETHICAL CONSIDERATIONS.....	42
12	STUDY FINANCES.....	42
12.1	FUNDING SOURCE.....	42
12.2	CONFLICT OF INTEREST	42
13	PUBLICATION PLAN.....	43
14	REFERENCES.....	43
15	ATTACHMENTS	50
15.1	INVESTIGATIONAL DRUG BROCHURE FOR AIR001	ERROR! BOOKMARK NOT DEFINED.
15.2	CHARTER FOR DATA SAFETY AND MONITORING BOARD	ERROR! BOOKMARK NOT DEFINED.
15.3	SCHEDULE OF ASSESSMENTS	50

LIST OF ABBREVIATIONS

AE	Adverse Event/Adverse Experience
CFR	Code of Federal Regulations
CRF	Case Report Form
DSMB	Data and Safety Monitoring Board
FDA	Food and Drug Administration
GCP	Good Clinical Practice
HIPAA	Health Insurance Portability and Accountability Act
IB	Investigator's Brochure
ITT	Intent to Treat
IND	Investigational New Drug Application
IRB	Institutional Review Board
IP	Investigational Product
PHI	Protected Health Information
PI	Principal Investigator
SAE	Serious Adverse Event/Serious Adverse Experience
SOP	Standard Operating Procedure

Study Summary

Title	Inorganic Nitrite To Amplify the Benefits and Tolerability of Exercise Training In Heart Failure With Preserved Ejection Fraction
Protocol Number	16-001467
Phase	Phase II
Methodology	
This is a randomized, blinded, placebo-controlled, two-stage, parallel-group clinical trial with all subjects receiving exercise training (ET) and randomized to either inorganic sodium nitrite or matching placebo.
 
The trial includes 2 stages. In stage I, which has been completed, patients received inhaled nitrite/placebo. In stage II, patients will receive oral nitrite/placebo.

Overall Study Duration	4 years
Subject Participation Duration	14 weeks
Single or Multi-Site	Single site
Objectives	To determine if sodium nitrite can improve the clinical responses to ET in subjects with heart failure and preserved ejection fraction (HFpEF).
Number of Subjects	100 (36 received inhaled nitrite/placebo in the completed stage I, up to another 64 will receive oral nitrite/placebo in stage II of the study)

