Diagnosis and Main Inclusion Criteria	
Heart failure with preserved ejection fraction (HFpEF) defined by clinical heart failure, normal EF ($\geq 50\%$) and at least one of the following:
 
 • Previous hospitalization for HF with radiographic evidence (pulmonary venous hypertension, vascular congestion, interstitial edema, pleural effusion) of pulmonary congestion or • Catheterization documented elevated filling pressures at rest or with exercise or • Elevated NT-proBNP (>400 pg/ml) or • Echo evidence of diastolic dysfunction/elevated filling pressures manifest by medial E/e' ratio ≥ 15 and/or left atrial enlargement and chronic treatment with a loop diuretic for signs or symptoms of heart failure
Study Product, Dose, Route, Regimen	
Stage I tested Inhaled, nebulized sodium nitrite (AIR001) 80 mg at least 4 hours apart three times daily during waking hours (i.e. 08:00, 12:00, 16:00).
 
Stage II is testing oral nitrite 40 mg tid capsules vs matching placebo capsules (same dosing frequency).

Duration of Administration	12 weeks
Reference therapy	Placebo
Statistical Methodology	Data will be analyzed according to ITT principles (assigned group regardless of study drug administration or compliance with ET benchmarks achieved). Primary hypotheses will be tested using a two-sample t-test on the change (baseline to 12 week). Testing will be stratified by route of administration.

1 Introduction

Heart failure with preserved ejection fraction (HFpEF) afflicts millions of older Americans and is associated with exercise intolerance, reduced quality of life (QOL), high health care costs, and increased mortality. People with HFpEF display increased cardiac filling pressures and inadequate cardiac output reserve to deliver blood to the body during exercise. Numerous lines of evidence have implicated abnormalities in nitric oxide-cyclic guanosine monophosphate (NO- cGMP) signaling as playing a key role in promoting these abnormalities. While there is currently no proven effective medical treatment for HFpEF, exercise training (ET) has been shown to improve aerobic capacity and QOL in this population.

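### The Summary stratifies the primary test by route but Section 7.3 does not, and on the 68 patients counted in Section 7.2 only the unstratified test comes near the stated 80% power

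*Combined protocol and SAP*

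**What the plan says.** **Study Summary, Statistical Methodology.** The primary hypotheses are tested with a two-sample t-test on change from baseline to week 12, and "Testing will be stratified by route of administration". The same entry says "Data will be analyzed according to ITT principles". The Number of Subjects entry records that "36 received inhaled nitrite/placebo in the completed stage I".

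**Section 7.2 (its heading runs into the text of 7.1).** The target of 68 patients with complete data is met by "combining the patients with complete data receiving inhaled placebo in Stage I (n=17) with another 51 patients in Stage II", the 51 being 17 on placebo and 34 on nitrite. Section 1.0 gives the same build-up and justifies it by expecting inhaled and oral placebo to perform alike.

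**Section 7.3.** The model is a regression of change in peak VO2: "An indicator variable will be used to indicate the randomized treatment assignment". The text equates this with a two-sample t-test. The pre-planned sensitivity model adds baseline peak VO2 and "BMI, Sex, and Age group strata through an extension of the regression model used for the primary analysis"; neither model has a route or stage term. The alternative hypothesis is that the change "will be different between the two randomized groups".

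**Section 7.1.** The protocol undertakes to give the details of the primary analysis itself. Other matters, including how "analysis sets are provided in the SAP", are left to a supplementary document whose text is not in the file reviewed.

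**The concern.** Route and stage are the same variable here: Stage I was inhaled, Stage II is oral. The Summary therefore asks for a comparison within stage, and Section 7.3 for one that ignores stage. Where both arms are spread similarly over the stages, the choice matters little. In the Section 7.2 set it matters a great deal, because every nitrite patient is in Stage II and only half of the placebo patients are.

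Two things are at stake. If the Summary governs, the stated 80% power is not delivered on that set. If Section 7.3 governs, a comparison in which half of the control group was not randomised alongside the treated group is labelled a comparison of two randomised groups.

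The reason given for pooling concerns the placebo formulation. The endpoint, however, is the change after a training programme that both arms receive. A home-based option was added in July 2020 (revision list; Section 6.2), after Stage I had ended. Leaving two primary tests in the current text also allows the choice to be made after the data are seen.

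**Working it through.** **Inputs.** Section 7.2: difference 1.5 ml/kg/min, two-sided alpha 0.05, power 80%, 34 per group; cited SDs of change 2.0 (placebo arm of a drug trial) and 2.2 (training arm of an exercise trial). The text does not say which SD was used.

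**1. Reproduce the plan's figure.** n per group = 2(1.960 + 0.842)² SD² / 1.5².
- SD 2.2: 33.8, so 34. This matches.
- SD 2.0: 27.9, so 28.

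SD 2.2 is therefore taken as the planning value, with 2.0 shown alongside.

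**2. Information on the 68.** For each stratum the information on the treatment effect is n1·n2/(n1 + n2), in units of 1/SD².
- Unstratified: 34 × 34/68 = 17.0, so SE = SD/√17 = 0.243 SD.
- Stratified by route: the inhaled stratum gives 0 × 17/17 = 0 and the oral stratum 34 × 17/51 = 11.33, so SE = SD/√11.33 = 0.297 SD.

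**3. Power for 1.5 (noncentral t).**

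| Test | SD 2.2 | SD 2.0 |
|---|---|---|
| Treatment only, 34 v 34 (df 66) | 79.1% | 86.1% |
| Treatment plus stage term, same 68 (df 65) | 61.8% | 70.1% |
| Stage II only, 34 v 17 (df 49) | 61.4% | 69.7% |

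The normal approximation that yields n=34 gives 80.3% for the first row at SD 2.2 and 63.1% for 34 v 17, so the gap does not come from the t calculation. The difference detectable with 80% power rises from 1.52 to about 1.86 (SD 2.2) or from 1.38 to about 1.69 (SD 2.0) when the stage term is added.

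**4. What the unstratified test carries.** Let δ be the mean change in Stage II minus that in Stage I under the same treatment. The nitrite mean contains δ and the pooled placebo mean (17/34)δ, so the estimate is off by 0.5δ, in either direction. No document gives δ; the values below are illustrative (simulated t-test, SD 2.2).

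| Size of δ (ml/kg/min) | Type I error | Power for 1.5 if δ runs against nitrite |
|---|---|---|
| 0.25 | 5.6% | 72% |
| 0.5 | 7.4% | 63% |
| 1.0 | 14.5% | 44% |

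**5. If Stage I nitrite patients also enter.** At most 36 − 17 = 19 can; 13 to 19 with complete data is assumed. With k of them, the information is 17k/(17 + k) + 11.33, that is 18.7 (k = 13) to 20.3 (k = 19). At SD 2.2, stratified power is:
- 83-86% if the effect is 1.5 by both routes;
- about 65% if the inhaled effect is 0.75;
- 40-42% if the inhaled effect is 0.

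The last two effects are assumptions. On this set the unstratified test carries only 34/(34 + k) − 0.5 = 0.22 to 0.14 of δ, and type I error at δ = 1.0 is about 5-7%.

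**6. Stage II count.** Section 7.2 needs 51 with complete data. Section 1.0 also says 51, then reports 14 already enrolled and requires another 47. If all 14 complete, that makes 61; 51 results only if 4 of the 14 count. Assuming the 14 were split 1:1 and the 47 are split 2:1, 61 would be about 38 v 23, with information 38 × 23/61 = 14.33 and power 72% (SD 2.2) or 80% (SD 2.0).

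**The case against.** **The analysis set may be defined elsewhere.** Section 7.1 defers analysis sets to the SAP, so a reader who inferred that the plan never defines its set would go too far. This stands. It does not remove the conflict over the test, because Section 7.1 places the details of the primary analysis in the protocol.

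**The low power depends on the set and the count.** A reader might infer that the trial has only 61% power. The documents do not support that as a general statement. It holds for the route-stratified test on 34 v 17. It does not hold for Section 7.3's test, for the set with Stage I nitrite patients if both routes work equally well, or for a Stage II of about 38 v 23.

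**The bias is hypothetical.** A reader might also infer that the type I error is really near 15%. That needs a between-stage shift of 1.0, about 43% of the whole cited training gain of 2.3, and nothing in the documents suggests one so large. Section 1.0 returns treatment to 12 weeks to match Stage I, and Section 6.2 says the home programme models the centre-based one. Against this, the 14 early oral patients were enrolled under a modification that had shortened the intervention to 10 weeks, and the exercise-capacity paragraph in Section 6 still gives week 10 for Stage II. The size remains unknown; the exposure to a shift is not in doubt.

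**A stage term undoes the pooling.** On the 68 it removes all 17 Stage I placebo patients from the treatment contrast, and the sponsor pooled them because recruitment was not feasible otherwise. This stands: requiring the stage term in the primary model would be a preference between two defensible choices.

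**Conclusion.** The point holds in a limited form. Two current passages give different primary tests. On the set that Section 7.2 counts, the Summary's test has 61-62% power (SD 2.2) or 70% (SD 2.0), and Section 7.3's has 79% or 86%. The stated 80% and the route-stratified test cannot both apply to that set.

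The price of the unstratified test is that half of any stage difference enters the estimate, and that a partly non-concurrent comparison is described as fully randomised. Whether this would distort the result cannot be judged from the documents.

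The conclusion rests on the 34 + 17 + 17 composition, on an SD of 2.0 to 2.2 common to both arms, and on a true difference of 1.5. It would change if the SAP brings Stage I nitrite patients into the primary test or if Stage II ends with more than 17 placebo patients. Severity: should-fix.

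**What to change.** 1. Bring the Summary and Sections 7.2 and 7.3 to one primary test, and state whether Stage I nitrite patients enter it. Align the SAP if it differs.
2. Then, according to the choice:
   - If the route-stratified test is kept on the Section 7.2 set, restate its power as about 61-62% (SD 2.2) to 70% (SD 2.0).
   - If the pooled unstratified test is kept, pre-specify the concurrent Stage II comparison (or, almost the same on this set, a stage/route term) as a sensitivity analysis. Give its power for the actual Stage II counts: 61-70% at 34 v 17. First reconcile Section 1.0's 14 enrolled plus another 47 with the 51 in Sections 1.0 and 7.2.
3. In Section 7.3, describe the pooled comparison as partly non-concurrent.

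The cost is wording in three places, one extra analysis, and a less favourable stated power for the stratified or concurrent comparison. No added enrolment is asked for.
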